4.1. RANDOMIZATION

No specific methods for assigning subjects will be used for this clinical investigation. A consecutive series of subjects at each site meeting all the eligibility criteria will be enrolled in this clinical investigation.

4.2. STATISTICAL INTERIM ANALYSES AND STOPPING GUIDANCE

Interim analyses will be performed on a yearly basis. The progress of the clinical investigation will be reported together with the interim results on the variable level according to the analysis plan.

As the primary endpoint analysis will only be conducted at the end of the clinical investigation, no adjustment of the significance level will be required.

There will be no stopping rules specified for this clinical investigation.

4.3. TIMING OF FINAL ANALYSES

The full final report with complete analyses, progress and conduct reporting will be created at the end of this clinical investigation.

4.4. TIMING OF OUTCOME ASSESSMENT

Subjects in this clinical investigation will be evaluated at Operative/Discharge, and at 3 Months, 6 Months and 12 Months after the index procedure. The follow-up evaluations will include assessment of device-related adverse events/incidents, evaluation per SF-36 PCS and MCS scores as well as clinical assessment of bone consolidation. Investigators should consider weight-bearing, pain and imaging when assessing bone consolidation. See the section below for visit windows and a list of assessments to be performed at each visit, given by the CIP.

Assessment	Operative/ Discharge	3 Months ^{a, b} (+/-2 weeks)	6 Months ^{a, b} (+/-3 weeks)	12 Months ^b (+/-4 weeks)		
Informed Consent	Xc					
Demographics & Medical History	Х					
Inclusion/Exclusion	Х					
Primary Diagnosis	Х					
Surgical Procedure	Х					
Clinical Assessment of Bone Consolidation ^{d, e}		Х	Х	Х		
SF-36v2 (PCS & MCS)	X f	Х	X ^g	X ^g		
Subject Disposition ^h		Х	Х	Х		
Device-Related Adverse Events/Incidents & Reoperations will be collected throughout the course of the Clinical Investigation.						

- a. Follow-up visit schedule to reflect Institutions' Standard of Care practices
- b. If the subject missed a visit and outside of visit window, every effort should be made to collect data instead of noting visit as missed. Visit windows are calculated from the index event, and not from the previous visit.
- c. Informed consent must be obtained prior to enrollment in the study (i.e., prior to performance of any study-related activities).
- d. Once bone consolidation is observed, assessment no longer needs to be conducted at the additional follow-up visits.
- e. Investigators should consider weight-bearing, pain and imaging when assessing bone consolidation.
- f. SF-36v2 evaluation must be collected post-informed consent. This can be collected post-fracture and prior to surgery or immediately post-surgery.
- g. If bone consolidation is previously observed at the previous follow-up visit, evaluation is to be collected via phone.
- h. Subject Disposition assessment would occur at any time point for subject withdrawal prior to the completion of the clinical investigation.

 Table 4.4: Assessments and Clinical Investigation Elements

In addition, the "Operative/Discharge" visit also includes Pre-operative data, which can also be recorded post-operatively, as defined in the CIP. Pre-operative- and operative data is aggregated as "Initial Assessment" in EDC frontend, but separately listed in EDC data exports for analysis. The pre-operative data is captured at "Primary Diagnoses" assessment, operative data at "Surgical Procedure" assessment. The SAP relates to the separate designation pre-operative- and operative assessment, as given by EDC export.

4.5. STATISTICAL SOFTWARE

Statistical Analysis will be performed using IBM SPSS, IBM SPSS Sample Power as well as established standard software packages (e.g. MS Excel).

4.6. MISSING DATA

The intent is to collect as complete a dataset as possible. Nevertheless, in some situations missing data cannot be avoided. The reports and tables therefore will show the number and percentage of missing cases for each analyzed variable in relation to the enrolled cases for each post-operative assessment.

Missing data will be reported for each variable or calculation (if any) and overall totals will be reported including the proportion of missing data (if any).

4.7. CONFIDENCE INTERVALS AND P-VALUES

The following acceptance / rejection criteria were used for this clinical investigation:

Parameter	Acceptance / rejection criteria
Confidence level (1-a)	0.95 (95%)
Significance level (α)	0.05 (5%)
Power $(1-\beta)$	0.80 (80%)
Beta-level (β)	0.20 (20%)
Confidence interval of mean	95%
p-value indicating significance	\leq 0.05

Table 4.7: Acceptance / Rejection Criteria

4.8. UNITS

See analysis chapter for details related to units used for the different variables and calculations.

In case of collection of variables with non-SI units (e.g. pounds instead to kilograms), conversion of such data into SI units (and vice versa) will be ensured and both results will be reported for the full set of available subjects next to each other in the interim/annual and/or final reports.

4.9. CALCULATIONS AND TRANSFORMATIONS

Distances between times and differences between score results will be calculated. For full details of variables used for calculations and the creation of new variables based on these calculations, see analysis chapter.

4.10. ASSUMTIONS

In case of deviation from assumptions (e.g. normality), non-parametric methods will be used for analysis. No transformation of such data will be performed.

5. Population and Progress

5.1. ANALYSIS POPULATION

It is expected, that during this clinical investigation only one population for Tibia will exist and all subjects will be analyzed "Per Protocol" (PP). However, it cannot be fully avoided that in theory subjects might need to be excluded from the PP population. In this occasion, there will be two groups being fully analyzed to ensure transparency and avoid bias.

The groups are defined as follows:

• Intent-to Treat Population

The Intent-to-Treat (ITT) Population is defined to be all enrolled subjects. An enrolled subject is a subject that has signed informed consent, all screening procedures have been successfully completed, is eligible and can receive treatment. The ITT population will not be analyzed for the annual reports and will only be included in the final report.

• Per Protocol Population

The Per Protocol (PP) Population is defined to be all subjects in the ITT Population with no major protocol violations. The protocol violations that will exclude a subject are as follows:

- The subject does not receive the T2 Alpha Tibia Nail
- The subject does not meet all eligibility criteria
- The subject has a protocol violation that is considered likely to affect subject outcomes.

After the clinical investigation has been completed, a review of the data will be conducted to determine which subjects are to be excluded from the PP population.

The following tables will be created for interim/annual and final reports related to the clinical investigation populations and progress:

Evaluation	Level of	Analysis Plan
Variable / Question	Measurement	Analysis Flan
All Forms – Overview & Progres	s Report	
Counting of available subjects Subject Population by Site (Variable(s): SITENUM; SUBID)	Qualitative, nominal	Proportions, frequencies, column and row totals, missing proportion (if any).
Counting of available subjects Subject Population by Visit (Variable(s): SITENUM; SUBID; VISITDT)	Qualitative, nominal	Proportions, frequencies, column and row totals, missing proportion (if any).
Counting of available subjects Subject Population by Visit and by Site (Variable(s): SITENUM; SUBID; VISITDT)	Qualitative, nominal	Proportions, frequencies, column and row totals, missing proportion (if any).

Table 5.1: Populations and Progress Tables List

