- d. Death: The discontinuation of a subject's participation in the clinical investigation due to death must be fully explained. All available information concerning the death should be provided. Removal of a subject from continued follow-up in the clinical investigation due to death will not be considered a device failure unless the death is directly caused by, or attributable to, the T2 Tibia Nailing System. Data collected up until the point of death will be included in the final analysis.
- e. Other: A subject may be withdrawn by the Investigator if he/she believes that it is in the best interest of the subject or the IRB/EC may determine that a subject's continued participation in the clinical investigation represents an unacceptable risk to the subject. The Sponsor must be notified immediately if this occurs. All data collected up until the point of withdrawal or IRB/EC determination will be included in the final analysis.

A subject may also be withdrawn if the subject is non-compliant with the clinical investigation procedures or visits, or if a selection criteria violation is noted after the subject received the clinical investigation treatment and it is determined that the subject should be discontinued. All data collected up until the point of withdrawal will be included in the final analysis.

10. Clinical Investigation Evaluations, Procedures and Assessments

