2.2. CLINICAL INVESTIGATION DESIGN

This investigation is a prospective, multicenter clinical investigation. It is anticipated that a total of 80 subjects will be enrolled at up to 5 sites. Enrollment is estimated to commence in Q4 of 2018. Neither subjects nor investigators are blinded to treatment and the clinical investigation includes a historical control which will be compared to the T2 Alpha Tibia Nailing System.

The enrollment period is expected to occur over 32 months. Total duration of enrollment, 12 month follow-up and analysis is expected to take 47 months. The clinical investigation has been designed to follow the surgeon's standard of care for tibia fractured subjects, in addition to a 12 month follow-up visit.

3. Research Goals

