3.1.1. Primary Analysis / Endpoint

This analysis is only part of the final report. The primary endpoint analysis will only be executed once at the end of the clinical investigation and will not be part of any interim or annual reports or presentations given in front of the final report.

The 12 months post-operative results for subjects implanted with the T2 Alpha Tibia Nailing System will be compared to Sanders et al: Semiextended intramedullary nailing of the tibia using a suprapatellar approach: radiographic results and clinical outcomes at a minimum of 12 months follow-up. J Orthop Trauma, 2014; Sun et al: The outcome comparison of the suprapatellar approach and infrapatellar approach for tibia intramedullary nailing. Int Orthop, 2016; and Chan et al: Suprapatellar Versus Infrapatellar Tibial Nail Insertion: A Prospective Randomized Control Pilot Study. J Orthop Trauma, 2016". Specifically, the SF-36 score results reported by Wang, et al. (2017), Sanders, et al. (2014), Sun, et al. (2016) and Chan, et al. (2016) will serve as the control groups for the T2 Alpha Tibia group.

Higher SF-36 PCS and MCS score results are linked to better subject results and vice versa.

The clinical investigation endpoint is non-inferiority to the control, meaning the clinical investigation result should be equal or better than the control. In this clinical investigation, an equal or better SF-36 score result means equal or greater (\geq). As only results from samples will be captured, results are mostly estimates of the true population parameter. These estimates vary by a certain area, where it is expected that the true population parameter falls within. Based on this, it is required to specify a lower limit for the acceptable difference or zone of indifference, denoted as - θ .

Hypotheses were developed to allow for a comparison of the 12 months post-operative SF-36 PCS to evaluate effectiveness / performance. The 12 months post-operative SF-36 PCS is the primary endpoint of this clinical investigation. Hypothesis tests will be one-sided with a significance level α of 5%.

Hypothesis	Equations	Interpretation	
Null (H ₀)	$A - B < -\theta$	Central tendency of A is inferior to	
	12 Alpha 11bia (A) – Control (B, pooled benchmark results) < $-\theta$	the central tendency of B.	
Alternative	$A - B \ge -\theta$	Central tendency of A is non-inferi	
(H ₁)	T2 Alpha Tibia (A) - Control (B, pooled benchmark results) $\geq -\theta$	to the central tendency of B.	

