Sun et.al.	SP	49.41	44.71	included
Sun et.al.	IP	43.21	43.81	included
Wang et.al.		79.10	77.00	excluded

Summary of explorative analysis is listed below:

Descriptives

			Statistic	Std. Error
SF-36 PCS Physical at 12	Mean		43,4840	1,98495
months post-op	90% Confidence Interval	Lower Bound	39,2524	
	for Mean	Upper Bound	47,7156	
	Median		43,2100	
	Std. Deviation		4,43849	
	Minimum		38,00	
	Maximum		49,41	
	Range		11,41	
	Interquartile Range		8,31	
SF-36 PCS Mental at 12	Mean		45,7040	,63333
months post-op	90% Confidence Interval	Lower Bound	44,3538	
	for Mean	Upper Bound	47,0542	
	Median		46,0000	
	Std. Deviation		1,41617	
	Minimum		43,81	
	Maximum		47,00	
	Range		3,19	
	Interquartile Range		2,74	

As the mean physical score (PCS) was slightly lower, it was used for the sample size calculation.

For the clinical investigation the one-sided 95% confidence interval will be applied.

Acceptance Criteria for S	Sample Size Calculation			
Significance Level (a)	0.05 (5%)			
Power (1-β)	0.80 (80%)			
Confidence Interval (CI)	0.95 (95%)			
Tails	1			
Path	Non-inferiority T2 Alpha Tibia (A) ≥ Benchmark (B, pooled	benchmark results)		
Hamadhasan Dain	Null (H ₀)	$A - B < -\theta$		
Hypotneses Pair	Alternative (H ₁)	$A - B \ge -\theta$		
Benchmark Timepoint	12 months post-operative			
Benchmark Mean	43.48 points SF-36 PCS at 12 months (IP an	d SP together)		
	No standard deviation results were given by Wang et al.	Chan et al., Sanders et al. nor by		
Benchmark Std. Dev.	• Only Sun et al. reported standard deviations at 12 months postoperative for SF-36 PCS of 6.27 for the SP and of 6.52 for the IP subgroup			
	As a worst-case, the double standard deviation for the sample size calculation $(2 * 6.52 = 13)$	on reported by Sun et al. was used 3.04 points)		
Benchmark 90% CI of Mean	Lower 90% CI: 39.25 (two-sided 90% CI e	quals a one-sided 95% CI)		

	Upper 90% CI: 47.72
Margin (-0)	Lower 90% CI of Benchmark: 39.25
Software Used	IBM SPSS Sample Power V3.0

IBM SPSS Sample Power Output

One goal of the proposed clinical investigation is to test the null hypothesis that the population mean is 39.25. The criterion for significance (alpha) has been set at 0.050. The test is 1-tailed, which means that only an effect in the expected direction will be interpreted.

With the proposed sample size of 61 subjects, the clinical investigation will have power of 80.0% to yield a statistically significant result.

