This computation assumes that the population from which the sample will be drawn has a mean of 43.48 with a standard deviation of 13.04. The observed value will be tested against a theoretical value (constant) of 39.25.

This effect was selected as the smallest effect that would be important to detect, in the sense that any smaller effect would not be of clinical or substantive significance.

A second goal of this clinical investigation is to estimate the mean in the population. On average, a clinical investigation of this design would enable us to report the mean with a precision (95.0% confidence level) of plus/minus 2.77 points.

The precision estimated here is the median precision. Precision will vary as a function of the observed standard deviation (as well as sample size), and in any single clinical investigation will be narrower or wider than this estimate.

- Eile View Option	ns Tools Scenarios	Help	- 2 .			_181
Group	Population Mean	Standard Deviation	N of Cases	Standard Error	95% Lo w er	95% Upper
T2 Alpha Tibia IP & S	P 43,48	13,04	61 🔆	1,67	40,71	46,25
Lower Cr bound or be		Ę.				
Alpha= 0,050, Tails= 1		l		F	² ower = 0,805	
Alpha= 0,050, Tails= 1	ver	! 	x	F	⁹ ower = 0,805	
Alpha= 0,050, Tails= 1 Summary - Pov For the given effe constant of 39,22 is 0,805.	ver ct size (population mean= 4 5), sample size (61), and al	43,48, tested ag pha (0,050, 1-tai	ainst a led), power	F	² ower = 0,805	
Alpha= 0,050, Tails= 1 Summary - Pov For the given effer constant of 39,21 is 0,805. This means that 8 effect, rejecting th The test is one-ta direction can be s	ver tot size (population mean= 4 5), sample size (61), and al 1% of studies would be exp ne null hypothesis that the p illed, which means that only statistically significant.	43,48, tested ag pha (0,050, 1-tai pected to yield a opulation mean i an effect in the r	ainst a led), power significant s 39,25, expected	ŗ	⁹ ower = 0,805	

Estimated drop-out rate is 20% which leads to the requirement of enrolling additional 13 subjects into the clinical investigation.

Sample Size	Overall number of subjects to be enrolled: 74 subjects (rounded up to 80 subjects)

Table 3.2: Sample Size Justification

4. Methods

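### Per-protocol exclusions are settled after completion, partly by judgement, with no masking of the review to 12-month PCS and no analysis set named to decide non-inferiority

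*SAP*

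**What the plan says.** SAP 5.1 and Protocol 11.2 are essentially the same on this point.

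- **Expected set.** All subjects are expected to be analysed per protocol. If anyone has to be excluded, PP and ITT are both fully analysed, with ITT in the final report only.
- **Exclusion criteria.** A subject leaves PP if the nail was not received, if eligibility was not met, or if this applies: "The subject has a protocol violation that is considered likely to affect subject outcomes". No list of such violations and no threshold is given.
- **Timing and basis.** After completion, "a review of the data will be conducted to determine which subjects are to be excluded from the PP population". The reviewers, the listings they use and a sign-off are not described. Protocol 19 places data freeze after the last assessment but does not place this review before it.
- **ITT.** This is all enrolled subjects, where an enrolled subject is, among other conditions, one who "is eligible and can receive treatment".
- **Withdrawal.** Protocol 9.3 allows withdrawal where "a selection criteria violation is noted after the subject received the clinical investigation treatment", and keeps the data collected up to that point in the final analysis.
- **Primary test.** SAP 3.1.1 compares 12-month PCS with 39.25 by a one-sample t-test or, if normality fails, a sign test, one-sided at 5%. It does not name the set that decides.

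**The concern.** Exclusions from an analysis set are safe when they are fixed without knowledge of the outcome. Here the stated order puts the decision after all outcomes exist, and one criterion asks whether a violation was likely to affect them. Nothing in either document keeps the 12-month scores from those who decide. SAP Table 6.5.2 marks the PCS summary at each follow-up visit for the annual as well as the final reports; only the primary test is withheld until the end.

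The design makes this matter more than usual. There is one treated group and a fixed comparator, so removing a few low scorers raises the mean directly and no concurrent arm can offset the shift. If PP then passed and ITT failed, the plan gives no rule for the conclusion.

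**Working it through.** **Inputs.** From SAP 3.1.1 and 3.2: one-sided α 0.05, assumed mean 43.48, SD 13.04, constant 39.25, margin 43.48 − 39.25 = 4.23, required n 61, 80 enrolled, 20% drop-out. Evaluable at target: 80 × (1 − 0.20) = 64. The documents give no expected number of violations or exclusions, so those below are assumptions.

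**Step 1: the plan's own figure.** One-sample t-test with noncentral t, noncentrality 4.23/13.04 × √61 = 2.53. Power is 0.8051 at n = 61 and 0.7992 at n = 60. This reproduces the stated 61 subjects and 80% (0.805 on the software screen).

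**Step 2: outcome-aware exclusions, t-test.** Normal data were simulated at a true mean of 39.25, where the test should reject 5% of the time. After k subjects are dropped, t = (mean − 39.25)/(s/√(n − k)) is compared with the 95th percentile of t on n − k − 1 degrees of freedom.

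| Which subjects are dropped | k = 1 | k = 2 | k = 3 |
|---|---|---|---|
| Lowest among 6 violators of 64, violations unrelated to PCS | 7.0% | 8.1% | 8.3% |
| Lowest among 10 violators of 64, violations unrelated to PCS | 7.5% | 9.6% | 11.0% |
| At random from the lowest 20 of 61 | 6.7% | 8.5% | 11.2% |
| Exactly the lowest of 64 (upper bound) | 9.6% | 15.5% | 22.7% |

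A repeat of the violator rows with 200,000 runs agreed within about 0.2 percentage points.

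**Step 3: the same upper bound under the sign test.** Dropping the lowest scores leaves the number above 39.25 unchanged but reduces n. With 64 subjects, 40 must lie above: probability 3.0%. With 63 the requirement is 39 (5.2%), with 62 it is 38 (8.4%), with 61 it is 38 (8.4%).

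**Step 4: shift of the mean, upper bound.** With SD 13.04 the lowest 1, 2 or 3 of 64 move the mean by about 0.5, 0.9 or 1.3 points; 1.3/4.23 is 31% of the margin. SD 13.04 is twice the only reported value. At 6.52 the shift for three is 0.65 points, or 15% of the margin. The error rates in Step 2 are practically unaffected by the SD.

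**Step 5: exclusions made without sight of PCS.** The error stays at 5.0% to 5.1% for 1 to 5 exclusions from 61. Power falls from 80.5% to 79.9% with one exclusion and 78.7% with three. Starting from 64, three exclusions leave 61 and hence 80.5%.

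**The case against.** The best defence is that nobody can be excluded for a low score alone. Non-receipt of the nail is a fact, eligibility is checked during monitoring (SAP 6.2), and the third criterion needs an actual violation. Deviations are recorded and reported to the ethics committees (Protocol 12) and listed in the annual and final reports (SAP 5.4). The pool of excludable subjects is therefore largely documented independently of PCS, and both sets are reported. This stands, and it is why the violator rows describe the risk better than the bottom row of the table. It does not remove the choice within the pool. Some eligibility criteria also need judgement, such as exclusions e, h and i in Protocol 9.2.

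Three stronger readings are tempting, and the documents do not support them.

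- *The reviewers will see every 12-month score.* This is inferred from silence. The statement "Neither subjects nor investigators are blinded to treatment" concerns treatment, not reviewers' access to outcomes. What can be said is that masking is not specified.
- *A treated subject later found ineligible drops out of both sets.* This is only one reading. PP is formed from ITT by removing ineligible subjects, a step with nothing to do if ITT had already lost them, and Protocol 9.3 keeps their data. SAP 5.2, which defines eligible as meeting all criteria, leaves an ambiguity that needs clarifying.
- *The sponsor will choose the favourable set.* The plan is silent on which set decides; it does not grant that choice.

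**Conclusion.** The concern holds in a limited form. The plan states a rule under which PP exclusions are decided late, partly by judgement and without specified masking, and it leaves the deciding set open. Reporting both sets makes a tilt visible but does not settle which result counts.

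Under the t-test, 1 to 3 outcome-aware exclusions give a true error of about 7% to 11% in place of 5%, if 6 to 10 of 64 subjects have violations unrelated to PCS and the lowest scorers among them are dropped. The 10%, 16% and 23% are an upper bound, since each of the very lowest scorers would also need a qualifying violation; under the sign test that bound is about 5% to 9%. All these rates describe the PP test taken alone. They show what the rule permits and do not predict what the reviewers will do. The point should be corrected because it touches the primary conclusion and cannot be credibly repaired once the scores have been seen.

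**What to change.** 1. In SAP 5.1 and Protocol 11.2, replace the sentence on the post-completion review with: *PP exclusions are decided and signed before data freeze, from the deviation and eligibility listings only, by reviewers without sight of SF-36 scores, using the list of major violations in this plan.* Add that list.
2. Name in advance the set or sets that decide non-inferiority. ITT alone, or both ITT and PP, would each close the gap.
3. State that eligibility in the ITT definition means judged eligible at enrolment, so that a treated subject later found ineligible stays in ITT, in line with Protocol 9.3.

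The cost is wording and an earlier date for a review that is already planned. No further subjects, visits or data are needed. Requiring both sets to pass would cost a little power where they differ.
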